5.1.3. Immunogenicity Visit Windows

For immunogenicity analysis, assessments will be allocated to an analysis visit based on the planned visit as captured in the eCRF. Visits that are out of the protocol-defined visit windows (see [Table 5](#) for ExPEC9V and [Table 6](#) for HI antibody titer immunogenicity analysis) will not be included in the PPII/PPEI immunogenicity analysis. However, they may be included in the sensitivity analyses based on FAS.

Table 5: Visit Windows for ExPEC9V Antibody Titers Immunogenicity Analysis

Group	Analysis time point label (relative to ExPEC9V vaccination)	Corresponding CSP visit day	Reference day	Target day (from reference day)	Window of target day (days)
CoAd group	Day 1	Day 1	Day of vaccination 1	1	(-8, 1]
	Day 30	Day 30	Day of vaccination 1	30	[23, 37]
	Day 59	Day 59	Day of vaccination 2	30	[23, 37]
Control group	Day 1	Day 30	Day of vaccination 2	1	(-8, 1]
	Day 30	Day 59	Day of vaccination 2	30	[23, 37]

Table 6: Visit Windows for HI Antibody Titers Immunogenicity Analysis

Analysis time point label (Relative to Flu vaccination)	Corresponding CSP visit day	Reference day	Target day (from reference day)	Window of target day (days)
Day 1	Day 1	Day of vaccination 1	1	(-8, 1]
Day 30	Day 30	Day of vaccination 1	30	[23, 37]

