## 5.5. Criteria for Temporarily Delaying Study Vaccine Administration

The following events constitute a temporary contraindication to study vaccination:

- Clinically significant acute illness at the time of vaccination. This does not include minor illnesses, such as diarrhea or mild upper respiratory tract infection.
- Fever (body temperature  $\geq 100.4^{\circ}\text{F}$  [ $38.0^{\circ}\text{C}$ ]) within 24 hours prior to the planned time of vaccination.
- An illness which in the judgment of the investigator may interfere with reactogenicity or safety assessments.
- Medically indicated vaccinations, including SARS-COV-2 vaccine boosters, taking into account the restrictions outlined in Section 5.2., Exclusion Criteria, and Section 6.8., Concomitant Therapy.

If any of these events occur at the scheduled time for the first vaccination, randomization at a later date within the screening period (allowed window up to 8 days) is permitted at the discretion of the investigator and after consultation with the sponsor. If randomization cannot occur within the screening window, rescreening is required.

If any of these events occur at the scheduled time for one of the subsequent vaccinations, the vaccination can be delayed up to 10 days on top of the allowed time window of Visit 3 ( $\pm 7$  days). The immunogenicity and safety assessments of Visit 3 should still be performed on the actual Day 30 ( $\pm 7$  days).

Vaccination may be delayed for reasons other than acute illness at investigator's discretion. Vaccination must be completed within the specified window and upon approval of the sponsor. A check of eligibility criteria may be repeated as necessary.

If the vaccination visit cannot be rescheduled within the allowed window or the contraindications to vaccination persist, the sponsor should be contacted for further guidance.

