## **8. STUDY ASSESSMENTS AND PROCEDURES**

### **Overview**

The [Schedule of Activities \(SoA\)](#) summarizes the frequency and timing of study visits and of immunogenicity and safety measurements applicable to this study.

If multiple assessments are scheduled for the same timepoint, it is recommended that procedures be performed in the following sequence: vital signs, other safety assessments, blood draws. If needed, assessments may be performed at another day within the applicable visit window. Actual dates and times of assessments will be recorded in the source document and/or in the eCRF.

At screening, participants will be specifically questioned regarding the medical history of UTI. This includes any uncomplicated, complicated, or recurrent UTIs that were diagnosed by a physician (or qualified healthcare provider) and that required antimicrobial therapy. The details will be collected in the eCRF. Note: a history of isolated male accessory gland infections will not be considered as a history of UTI.

Participants will be provided a thermometer (to measure body temperature), ruler (to measure local injection site reactions), and participant eDiary to record body temperature and solicited local (at injection site) and systemic signs and symptoms.

The eDiary includes instructions on how to capture the signs and symptoms and grading scales to assess severity. The study staff is responsible for providing appropriate training to the participant to avoid missing or incorrect data. The eDiary will be reviewed by study personnel at visits indicated in the [Schedule of Activities \(SoA\)](#). If the eDiary review is missed, the eDiary will be reviewed during the following visit. If a participant misses a vaccination, the eDiary covering the period after the missed vaccination does not have to be completed.

The total blood volume to be collected from each participant will be approximately 90 mL.

Repeat or unscheduled samples may be taken for safety reasons or for technical issues with the samples.

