### **Visit Windows**

Visit windows are provided in the Schedules of Activities.

The timings of the post-vaccination visits will be determined relative to the actual day of the corresponding vaccination. If a participant misses a vaccination, the post-vaccination visits will be calculated from the imputative vaccination date according to protocol.

Note: In case any of the criteria for temporarily delaying study vaccine administration (see Section 7.1., Discontinuation of Study Vaccination) are met at Visit 3 (Day 30), this visit would need to be split into 2 visits. The administration of the second study vaccination can be delayed up to 10 days on top of the allowed time window of Visit 3 ( $\pm 7$  days). The immunogenicity and safety assessments of Visit 3 should still be performed on the actual Day 30 ( $\pm 7$  days).

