5.1.1. Study Phases

The immunogenicity baseline (or reference) value for the two groups is determined as follows. For CoAd group, the baseline value of the HI and ExPEC9V antibody titers will be the value of the last available assessment prior to the vaccination on Day 1. For the Control group, the baseline value for the HI and ExPEC9V antibody titers will be the value of the last available assessment prior to the vaccination on Day 1 and Day 30, respectively.

If a participant received at Day 1 both vaccinations but the start date-time of one of the vaccinations is not available in the clinical database, this date-time will be imputed with the date-time of the other vaccination.

The safety analysis will present all results by phase. Immunogenicity results will be presented per scheduled time point as appropriate. Listings may be shown per phase and time point.

Study day or relative day is defined as follows:

- Study Day = visit date – date of Day 1 + 1; if visit date \geq date of Day 1 (date of first vaccination).
- Study Day = visit date – date of Day 1; if visit date < date of Day 1 (date of first vaccination).

For ExPEC9V immunogenicity endpoints in the Control group, the day of the second vaccination will be considered as Day 1 in Post-dose 2.

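### SAP Table 5 puts protocol-compliant Control-group ExPEC9V baselines out of window when dose 2 is delayed, and conflicts with the SAP's own baseline definition

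*SAP*

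**What the plan says.** **Protocol, Section 5.5** (also the Schema and Schedule of Activities footnotes): if a temporary contraindication is present at Visit 3, "the vaccination can be delayed up to 10 days on top of the allowed time window of Visit 3", which is ±7 days around Day 30. The blood draw does not move with the dose: "The immunogenicity and safety assessments of Visit 3 should still be performed on the actual Day 30", again ±7 days. Under Visit Windows in Section 8, "this visit would need to be split into 2 visits". The Schedule of Activities has three 30 mL immunogenicity draws, and the Section 8 Overview gives the matching total: "The total blood volume to be collected from each participant will be approximately 90 mL". No redraw is scheduled on a postponed dose day.

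**SAP, Section 5.1.3, Table 5**: the protocol Day 30 sample is the Control group's Day 1 (baseline) sample for ExPEC9V titers. Its reference day is vaccination 2 and its window is (-8, 1]. Visits outside the windows "will not be included in the PPII/PPEI immunogenicity analysis". They may be used in sensitivity analyses on the full analysis set.

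**SAP, Section 5.1.1**: the Control baseline for HI and ExPEC9V titers is "the value of the last available assessment prior to the vaccination on Day 1 and Day 30, respectively". No window is attached. Sections 5.3.2 and 5.4.4 repeat the last-pre-vaccination definition, also without a window.

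**The concern.** The SAP describes its windows as the protocol's. The protocol's window for this blood draw, however, runs ±7 days around Day 30 counted from vaccination 1, whereas Table 5 counts back from vaccination 2. When dose 2 is postponed, a site that follows the protocol exactly can produce a sample that the SAP treats as out of window. The SAP foresees the split visit, since Table 4 has rules for a Day 30 visit that precedes the second dose, but Table 5 does not carry that case through.

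The mechanism works in one arm only. The CoAd baseline is referenced to vaccination 1, so a delay of dose 2 cannot move it out of window. The loss is also unlikely to be unrelated to health: the reasons for delay listed in Protocol Section 5.5 are acute illness, fever, an interfering illness or another indicated vaccination, although delay for other reasons is also allowed at the investigator's discretion.

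At stake are the outputs that need a baseline. A Control participant with a valid post-vaccination titer would drop out of them because a baseline collected as instructed was set aside.

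**Working it through.** **The plan's power figures (Protocol Section 9.2), checked first.** Inputs: 419 evaluable per group, margin log10(1.5) = 0.1761, SD 0.6 (O-serotype) and 0.5 (HI), two-sided 5%.

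- Power for one comparison = Φ(0.1761 / (SD × √(2/419)) − 1.96).
- O-serotype: 98.89% for one antigen; to the power 9, 90.47%. A noncentral t with 836 degrees of freedom gives 98.88% and 90.35%. The plan states 98.88% and 90.36%.
- HI: 99.91% for one strain; to the power 4, 99.66% (noncentral t 99.65%). The plan states 99.91% and 99.64%.
- Enrolment: 419 / 0.90 = 465.6, rounded up to 466, as stated.

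The plan's figures reproduce. They concern the primary comparison, whose model contains group, age category and UTI history but no baseline titer.

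**Date arithmetic**

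1. Visit 3 blood: Day 30 ±7, so Day 23 to Day 37.
2. Latest dose 2: 30 + 7 + 10 = Day 47.
3. Relative day. For Control ExPEC9V endpoints "the day of the second vaccination will be considered as Day 1 in Post-dose 2". Section 5.1.1 counts a sample before the reference day as sample date minus reference date. A gap of 7 days is relative day -7, inside (-8, 1]. A gap of 8 days is relative day -8, which the open bracket excludes.
4. Results:

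| Blood drawn on | Longest gap (dose on Day 47) | Dose days that keep the baseline | Dose days that lose it |
|---|---|---|---|
| Day 23 | 47 − 23 = 24 days | up to Day 30 | Days 31–47 |
| Day 30 | 47 − 30 = 17 days | up to Day 37 | Days 38–47 |
| Day 37 | 47 − 37 = 10 days | up to Day 44 | Days 45–47 |

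Anyone bled on or before Day 30 and dosed in the extra 10-day period (Days 38–47) is out of window. Of the 15 × 10 = 150 pairings of a sample day (23–37) with a dose day (38–47), 122 are out of window. That is a count of date pairs, not a forecast.

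**Which analyses use the sample**

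- Not affected: the primary ANOVA (no baseline term); PPEI membership (O-antigen data for at least one serotype, not a baseline); the Control post-dose sample (windowed from vaccination 2, so it moves with the dose).
- Affected: the baseline-adjusted sensitivity analyses for ECL (Section 5.3.2) and MOPA (Section 5.4.4); the proportions with at least 2-fold and 4-fold rises, GMR and baseline GMT (Section 5.4.4); and the analysis by baseline LLOQ status named in the SAP version history.

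**Illustration of size.** The documents give no rate of delayed dose 2, so these loss rates are assumptions. The calculation takes SD 0.6, 419 CoAd participants, independent comparisons, normal approximation and no precision gain from adjustment: power = [Φ(0.1761 / (0.6 × √(1/419 + 1/n)) − 1.96)]^9.

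| Control baselines lost | Control n | All-nine power, adjusted analysis |
|---|---|---|
| 0% | 419 | 90.5% |
| 2% | 411 | 90.0% |
| 5% | 398 | 89.1% |
| 10% | 377 | 87.4% |
| 20% | 335 | 83.0% |

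**The case against.** The strongest reply is that nothing need be lost. The SAP gives an unwindowed baseline definition in three places, two of them in the sections that specify the baseline-adjusted analyses. Section 5.1.3 also allocates samples by planned visit, and a sample at Day 30 ±7 lies within the protocol's own window. A programmer could follow those statements and keep every sample. This stands in part: loss is not certain. But Table 5 gives an explicit numerical window for this very sample and excludes what falls outside it, and the SAP does not say which rule yields. Two programmers could produce different PPEI baselines.

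A second reply is that the Protocol Synopsis and Section 4.1 describe blood being taken before vaccination on each vaccination day, which would leave no gap. The specific rule for a delayed dose says otherwise, and the schedule has no extra draw.

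A third reply is that the effect is limited. This largely stands. The 24-day gap needs the earliest draw with the latest dose, gaps of up to 7 days lose nothing, minor illnesses do not trigger a delay, and full analysis set sensitivity analyses may include the sample. A modest loss also costs little power in the adjusted analysis.

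A reader might go further and infer that the trial's success criterion is at risk, or that the fold-rise and GMR comparisons are biased by a known amount. The documents support neither. The primary model does not use baseline, and no direction or size of bias can be derived from what is given.

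**Conclusion.** The point holds within limits. Followed as written, Table 5 removes protocol-compliant Control baselines from the PPEI analysis whenever the Visit 3 blood precedes dose 2 by 8 to 24 days. Delay of dose 2 has no such effect in CoAd. This conflicts with the SAP's own baseline definition, and no precedence is stated. The consequences are confined to sensitivity and secondary outputs; the primary non-inferiority conclusion and its power are untouched.

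The size is unknown, because it depends on how often dose 2 is delayed far enough. The power loss in the illustration is small at 5% (90.5% to 89.1%). The better reason to correct the rule is that the missingness would be one-sided and probably related to health. The conclusion rests on reading (-8, 1] with the relative-day convention of SAP Section 5.1.1, and on no redraw being taken on the delayed dose day.

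**What to change.** In SAP Table 5, define the Control Day 1 baseline as the last sample before vaccination 2 taken within the protocol's Visit 3 window (Day 30 ±7, counted from vaccination 1). Alternatively, add a sentence to Section 5.1.3 stating that the baseline definition in Section 5.1.1 overrides Table 5.

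Do not simply widen the window to [-24, 1]. It would admit, for example, a Day 16 sample with a Day 40 dose (40 − 16 = 24), and Day 16 is outside Day 30 ±7.

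The cost is one table cell or one sentence. The small downside is that some Control baselines will be up to 24 days old at dose 2 rather than at most 7; flagging those with gaps of 8 days or more in a listing would make this visible. The change concerns the analysis rule only and implies no change to vaccination timing or blood sampling.

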5.2. Participant Dispositions

Participant information will be shown in the appropriate analysis sets.

The number of participants in the following disposition categories will be summarized throughout the study by intervention group or overall, as appropriate.

- participants in the AS set (overall only)
- participants in the Randomized set
- participants vaccinated and not randomized
- participants randomized and not vaccinated
- participants not randomized and not vaccinated (overall only)
- participants in the FAS
- participants in the PPII set at each visit after administration of flu vaccine
- participants in the PPEI set at each visit after administration of ExPEC9V vaccine
- participants who discontinued study
- participants who discontinued second vaccination
- reasons for premature termination of the study
- reasons for discontinuation of second vaccination

Also, the number of participants and percentage per phase will be tabulated.

The number of participants in each of the stratification stratum in the IWRS (as stratified) will be compared to the number reported in the eCRF (as collected).

Other participant information variables: demographics and baseline characteristics, major protocol deviations, and concomitant medications will be analyzed as described in [Appendix 1](#), [Appendix 2](#) and [Appendix 3](#), respectively. Medical history and concomitant diseases will be tabulated or presented in a listing, as appropriate.

5.3. Primary Endpoint(s) Analysis

5.3.1. Definition of Endpoint(s)

The primary endpoints are:

- HI titers against each of the 4 influenza vaccine strains at 29 days after the administration of a HD quadrivalent seasonal influenza vaccine and
- Multiplex ECL-based immunoassay antibody titers at 29 days after the administration of ExPEC9V vaccine.

5.3.2. Analysis Methods

The primary immunogenicity objectives will be assessed by calculating the following CI.

- The 2-sided 95% CIs for the difference in \log_{10} -transformed HI antibody titers against each of the 4 influenza vaccine strains at 29 days after the administration of the HD quadrivalent seasonal influenza vaccine between the Control and the CoAd groups.
- The 2-sided 95% CIs for the difference in \log_{10} -transformed O-serotype antibody titers against each of the 9 O-serotypes at 29 days after the administration of ExPEC9V vaccine between the Control and the CoAd group.

For HI antibody titers against each of the 4 influenza vaccine strains and for O-serotype antibody titers against each of the 9 O-serotypes, an analysis of variance (ANOVA) model will be fitted with the respective titers as dependent variable, and group (Control or CoAd), age category (≥ 65 to < 75 and ≥ 75 years) and history of UTI (yes/no) as independent variables. Based on these ANOVA models, the CIs around the difference will be calculated and will be back transformed (by exponentiation) to CIs around a GMT ratio ($\text{GMT}_{\text{Control group}}/\text{GMT}_{\text{CoAd group}}$) and compared to the non-inferiority margin of 1.5.

Only if the upper bound of the 2-sided 95% CI for the GMT ratio (Control group/CoAd group) of the HI antibody titers for each of the 4 vaccine strains and of the O-serotype antibody titers for each of the 9 O-serotype antigens lies below 1.5, non-inferiority of co-administration versus separate administration will be concluded for both vaccines (HD quadrivalent seasonal influenza vaccine and ExPEC9V). If 1 or more confidence limits for the GMT ratio exceed 1.5, non-inferiority cannot be concluded.

As a sensitivity analysis to assess the impact of baseline titers, the primary endpoint will also be evaluated adjusting for the respective baseline titers. For immunogenicity, baseline is considered as the last assessment prevaccination. In a second sensitivity analysis, different variances between the groups will be allowed. Therefore, the CIs will be calculated via Welch's ANOVA.

The primary analysis will be based on the stratification factors, age group and history of UTI reported in the database, as collected in the eCRF. Supportive analyses for non-inferiority will be performed by age group and history of UTI as stratified in IWRS.

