The present study also aims to include participants (aged  $\geq 65$  years) with and without a previous history of UTI to allow a comparison of vaccine-elicited immunogenicity between the 2 populations (ie, with a previous UTI history versus without a previous UTI history). Participants with a previous UTI history, particularly if some of the UTIs were attributable to *E.coli* infection, have been observed to elaborate higher baseline immune responses targeting *E.coli* O-antigens, as shown in the VAC52416BAC1001 study Cohort 2 (see Section 2.2., Background). This observation needs to be further investigated through a comparison of immunogenicity elicited by the vaccine for the 2 aforementioned populations.

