## 9.2. Sample Size Determination

Sample size calculations are performed under the following assumptions:

- No effect of co-administration of ExPEC9V and seasonal influenza vaccine on the immune response against influenza as measured by HI antibody titers against the 4 influenza vaccine strains at 29 days after the administration of influenza vaccine
- A standard deviation of 0.5 at the log10 scale for HI antibody titers against the 4 influenza vaccine strains at 29 days after the administration of influenza vaccine (with or without ExPEC9V)
- No effect of co-administration of ExPEC9V and seasonal influenza vaccine on the immune response against the O-serotype antigens as measured by antibody titers against the 9 O-serotype antigens at 29 days after the administration of ExPEC9V
- A standard deviation of 0.6 at the log10 scale for ExPEC9V antibody titers at 29 days after the administration of ExPEC9V (with or without seasonal influenza vaccine)
- A non-inferiority margin of 1.5
- 2-sided  $\alpha$  of 5%

---

 Non-inferiority criteria based on FDA guidance for influenza vaccines ([FDA 2007b](#)).

A total of 419 evaluable participants per group are needed to have 99.91% power to show non-inferiority in HI antibody titers for 1 influenza vaccine strain and to have 98.88% power to show non-inferiority in antibody titers against 1 O-serotype antigen. With this sample size, the overall power to show non-inferiority in HI antibody titers against each of the 4 influenza vaccine strains at 29 days after the administration of seasonal influenza vaccine as well as non-inferiority in antibody titers against each of the 9 O-serotype antigens at 29 days after the administration of ExPEC9V is at least 90% (see table below).

	1 comparison	All comparisons
Flu NI (SD=0.5)	99.91%	99.64% (4 comparisons)
ExPEC9V NI (SD=0.6)	98.88%	90.36% (9 comparisons)
Total		> 90% power

To account for 10% exclusions from the per protocol set (see below for definitions of analysis sets), drop-outs and missing samples, approximately 466 participants per group should be enrolled, resulting in a total sample size of approximately 932 participants.

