### 9.4.3. Immunogenicity Analyses

The primary immunogenicity objectives will be assessed by calculating:

- The 2-sided 95% CIs for the difference in  $\log_{10}$ -transformed HI antibody titers against each of the 4 influenza vaccine strains at 29 days after the administration of the HD quadrivalent seasonal influenza vaccine between the Control and the CoAd group.
- The 2-sided 95% CIs for the difference in  $\log_{10}$ -transformed O-serotype antibody titers against each of the 9 O-serotypes at 29 days after the administration of ExPEC9V between the Control and the CoAd group.

For HI antibody titers against each of the 4 influenza vaccine strains and for O-serotype antibody titers against each of the 9 O-serotypes, an ANOVA model will be fitted with the respective titers as dependent variable and group (Control or CoAd), age category, and history of UTI (as stratified) as independent variables. Based on these ANOVA models, the CIs around the difference will be calculated and will be back-transformed (by exponentiation) to CIs around a GMT ratio ( $\text{GMT}_{\text{Control group}}/\text{GMT}_{\text{CoAd group}}$ ) and compared to the non-inferiority limit of 1.5.

Only if the upper bound of the 2-sided 95% CI for the GMT ratio (Control group/CoAd group) of the HI antibody titers for each of the 4 vaccine strains and of the O-serotype antibody titers for each of the 9 O-serotype antigens lies below 1.5, non-inferiority of co-administration versus separate administration will be concluded for both vaccines (seasonal influenza vaccine and ExPEC9V). If 1 or more confidence limits for the GMT ratio exceed 1.5, non-inferiority cannot be concluded.

As a sensitivity analysis to assess the impact of baseline titers, the primary endpoint will also be evaluated adjusting for the respective baseline titers. For immunogenicity, baseline is considered as the last assessment prevaccination. In a second sensitivity analysis, different variances between the groups will be allowed. Therefore, the CIs will be calculated via Welch's ANOVA.

Seroconversion is defined for each of the 4 influenza vaccine strains at 29 days after the administration of a seasonal influenza vaccine as:

- HI titer  $\geq 1:40$  in participants with a prevaccination HI titer of  $< 1:10$ , or
- a  $\geq 4$ -fold HI titer increase in participants with a prevaccination HI titer of  $\geq 1:10$

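### The primary non-inferiority model omits the prevaccination titer. Adding the Day 1 titer in both groups would probably narrow all 13 decisive intervals, but the SAP's own baseline definition is unsuitable for the nine O-serotype models.

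*SAP*

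**What the plan says.** SAP 5.3.2 and protocol 9.4.3 fit one ANOVA per titer, with group, age category and history of UTI as the independent variables. Non-inferiority is concluded only if all 13 upper 95% limits for the Control/CoAd GMT ratio lie below 1.5.

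Baseline titer has a secondary role in both documents. SAP 5.3.2: "As a sensitivity analysis to assess the impact of baseline titers, the primary endpoint will also be evaluated adjusting for the respective baseline titers". Protocol 9.4.3 likewise: "the primary endpoint will also be evaluated adjusting for the respective baseline titers".

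Protocol 4.1 and the Schedule of Activities plan prevaccination blood for all participants on Day 1 and Day 30. Protocol section 3 lists ECL titers on Days 1, 30 and 59 as an endpoint.

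SAP 5.1.1 and Table 5 define the ExPEC9V baseline differently by group: the Day 1 sample in CoAd and the Day 30 sample in Control. For HI titers it is Day 1 in both groups.

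On the strata, protocol 9.4.3 specifies "history of UTI (as stratified) as independent variables". SAP 5.3.2 bases the primary analysis on factors "reported in the database, as collected in the eCRF", with the IWRS version supportive.

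**The concern.** A covariate measured before vaccination and correlated with the outcome reduces residual variance at almost no cost with about 838 evaluable participants. In a linear model on log10 titers it does so without changing the quantity estimated. The sponsor has some reason to expect baseline to matter for the O-antigens: protocol 2.1 says that participants with prior UTI "have been observed to elaborate higher baseline immune responses targeting" *E. coli* O-antigens. Yes/no UTI history is then a coarse stand-in for a titer that the trial measures directly.

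The stakes come from the success rule. One failed limit out of 13 fails the study, and planned power has almost no room above 90%. Nearly all the planned risk of failure lies with the nine O-serotypes.

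**Working it through.** **Inputs.** From protocol 9.2: "A non-inferiority margin of 1.5", so log10(1.5) = 0.1761; "A standard deviation of 0.5 at the" log10 scale for HI; "A standard deviation of 0.6 at the" log10 scale for O-serotypes; 419 evaluable per group; true ratio 1; two-sided 5%. The correlation ρ between baseline and Day 30 titer, net of age and UTI history, is not in the documents and is assumed.

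**1. Reproduce the plan.** The standard error is SD × √(2/419): 0.0345 (HI) and 0.0415 (O-serotype). The non-centrality is 0.1761/SE: 5.10 and 4.25. The non-central t with 836 df gives 99.91% and 98.88%, matching the protocol. Treating comparisons as independent:

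- four strains: 0.99913⁴ = 99.65% (protocol 99.64%)
- nine serotypes: 0.98879⁹ = 90.35% (protocol 90.36%)
- all 13: 90.04%

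The O-serotype half-width is 1.963 × 0.0415 = 0.081 log10, a factor of 1.21. An observed ratio above about 1.24 would fail.

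**2. Add a baseline covariate.** The residual SD becomes SD × √(1 − ρ²). The same power formula gives, at 419 per group:

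| ρ (assumed) | CI width | One serotype | Nine serotypes | All 13 | Nine, true ratio 1.05 | Equivalent n, 1/(1 − ρ²) |
|---|---|---|---|---|---|---|
| 0 (as planned) | 1.000 | 98.88% | 90.3% | 90.0% | 70% | 1.00 |
| 0.1 | 0.995 | 98.94% | 90.9% | 90.6% | 71% | 1.01 |
| 0.3 | 0.954 | 99.36% | 94.4% | 94.2% | 79% | 1.10 |
| 0.5 | 0.866 | 99.84% | 98.5% | 98.5% | 92% | 1.33 |
| 0.6 | 0.800 | 99.96% | 99.6% | 99.6% | 97% | 1.56 |

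**3. Relax independence.** With equally correlated normal test statistics, nine-serotype power as planned is about 92%, 93% and 95% for assumed between-serotype correlations of 0.3, 0.5 and 0.7. At 0.5, a baseline correlation of 0.3 raises it from about 93% to about 96%, a smaller gain than in the table.

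**4. Check which baseline would enter.** The SAP 5.1.1 Control value for O-serotypes is drawn after randomization, influenza vaccine and placebo; the CoAd value is drawn before any vaccine. If the Control sample were shifted upward by δ between Day 1 and Day 30, with no effect on the outcome, the adjusted Control − CoAd difference would move by −slope × δ. With equal SDs the slope equals ρ. For an illustrative δ of 0.05 log10 and ρ of 0.3, 0.5 and 0.7, that is −0.015, −0.025 and −0.035. A simulation with 419 per group gave −0.013, −0.024 and −0.035. The sign favours non-inferiority. The documents do not say that such a shift occurs; using Day 1 in both groups removes the question.

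**5. Check missing baselines.** PPII and PPEI membership (SAP section 4) does not name a baseline value, the 10% allowance in protocol 9.2 includes missing samples, and SAP 5.3.3 imputes no missing titers. A complete-case adjusted model gains only if ρ² exceeds the fraction of participants lost: 1% at ρ = 0.1, 9% at ρ = 0.3 and 25% at ρ = 0.5.

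**The case against.** The strongest reply is that nothing here is an error. The unadjusted intervals are valid, chance baseline imbalance is already covered by their width, the power target is met under the plan's assumptions, and the baseline-adjusted analysis is prespecified for all 13 endpoints. This stands, and it limits the point to lost efficiency.

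The size of the gain is also uncertain. No correlation is documented. Protocol 2.1 speaks only of O-antigen baselines and says nothing about HI. Baselines below LLOQ, set to a constant, would weaken a linear covariate, and UTI history in the model may already carry part of the information. At ρ = 0.1 the gain is negligible. All of this stands, and it is why a range is shown.

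A reader might infer that the two existing analyses need only exchange roles. That is sound for the four HI models, but not for the nine O-serotype models, where it would place an asymmetric post-randomization covariate in the decisive test.

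A reader might also infer that every participant has a baseline value. The documents support only that one is scheduled for everyone.

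**Conclusion.** The point holds as a recommendation on efficiency. The primary model leaves out a scheduled prevaccination measurement that would narrow the decisive intervals by a factor of √(1 − ρ²): about 0.5% at ρ = 0.1, 5% at 0.3, 13% at 0.5 and 20% at 0.6. Nine-serotype power at a true ratio of 1.0 rises accordingly from 90.3% to between 90.9% and 99.6%. These figures rest on the plan's SDs, 419 evaluable per group, independent comparisons, an assumed ρ, and no outcomes lost to missing baselines.

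The documents do not support reading this as invalid intervals or as a shortfall against the stated power. The difference between protocol and SAP over the source of the strata is real, but it is a separate alignment matter. The SAP version history gives its reason for specifying the source, and the difference neither strengthens nor weakens the case for baseline adjustment.

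**What to change.** Before unblinding:

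1. Make the primary model, for each of the 13 titers, log10 titer = group + age category + UTI history + log10 Day 1 titer. Take the Day 1 prevaccination sample in both groups, and state that the SAP 5.1.1 Control-group Day 30 baseline is not used as this covariate.
2. Keep the present ANOVA without baseline as the sensitivity analysis.
3. Add a rule for missing Day 1 titers, for example imputing the overall mean across both groups for the covariate only, as a stated exception to SAP 5.3.3, so that no outcome is dropped.
4. Separately, reconcile protocol 9.4.3 (strata as randomised) with SAP 5.3.2 (as collected in the eCRF), so that both name the same source for the primary model.

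The cost is wording in protocol 9.4.3 and SAP 5.3.2 and 5.3.3, plus a new covariate definition for the O-serotype models. Table 5 does not map the Control group's Day 1 visit, so it needs a row for it. No new sample is needed, since Day 1 ECL titers are already a protocol endpoint. The sample size can stay as it is, with the gain held as reserve.
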